	
subjects treated at Johns Hopkins, approximately 50% of NMO/NMOSD subjects improve from a relapse with steroids alone. The other 50% require escalated care with plasma exchange.
 
Plasma Exchange Treatment Phase
 
Should subjects not meet above clinical criteria to be discharged home, escalation to treatment with plasma exchange is standard of care.
 
The plasma exchange treatment phase begins at the end of the Steroid Treatment Phase and will last up to 14 days. During the Plasma Exchange Treatment Phase, subjects will undergo 1.0 – 1.5 volumes of plasma exchange every other day according to standard of care. At the end of this phase, a second MRI may be performed to compare to admitting MRI. If any further acute immunosuppressive treatment for the acute NMO flare is required and provided according to standard of care, the subject will continue to be followed for safety issues, but the clinical efficacy data will not be included in the statistical analysis. Historically among NMO/NMOSD patients treated at the Johns Hopkins Hospital, approximately 95% of NMO/NMOSD patients who complete plasma exchange are discharged following completion of the plasma exchange.
 
Follow-up
 
Every month after discharge, subjects will be followed with monthly B cell counts until their B cell counts replete to a minimum of 0.5% for patients who will continue to be treated with B-cell depleting agents for preventive care, according to standard of care, or to a minimum of 5% for patients who will use other preventive strategies. In addition, complete blood counts with differential to track neutrophil counts and complete metabolic profiles will be completed monthly as well.
 
The secondary efficacy outcome is neurologic function at follow up 90 days and 6 months after initial hospitalization for the acute relapse. In addition to a thorough history and physical examination, including EDSS rating, visual examination and timed walk, a research MRI of the spine will be performed at day 90 to compare to the relapse lesion.

Trial visits	Screening (Day 0), Steroid Treatment Phase (Days 1 to 5), Plasma Exchange Treatment Phase, if necessary (Days 6 to 20), and Follow-up (monthly blood tests and visits on Days 90 and 180).

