	
 a. Corticosteroids b. Diphenhydramine c. Murine or mouse/human chimeric antibodies 
4. Past or current malignancy, except for
 
 a. Cervical carcinoma Stage 1B or less b. Non-invasive basal cell and squamous cell skin carcinoma c. Cancer diagnoses with a duration of complete response (remission) >5 years 
A history of hematologic malignancy excludes a subject from participation, regardless of response.
 
5. Significant concurrent, uncontrolled medical condition including, but not limited to, cardiac, renal, hepatic, hematological, gastrointestinal, endocrine, immunodeficiency syndrome, pulmonary, cerebral, psychiatric, or neurological disease which could affect the subject's safety, impair the subject's reliable participation in the trial, impair the evaluation of endpoints, or necessitate the use of medication not allowed by the protocol, as determined by the PI of the trial.
 
6. Use of an investigational drug or other experimental therapy for a condition other than NMO within 4 weeks, 5 pharmacokinetic half lives or duration of biological effect (whichever is longer) prior to screening.
 
7. Current participation in any other interventional clinical trial. Participation in non-interventional trial requires approval of the protocol by investigator.
 
8. Subjects who are concurrently receiving any other investigational agents, or have participated in an interventional clinical trial within the last 21 days, or subjects who have been vaccinated with a live vaccine < 2 months prior to trial inclusion.
 
9. Because there is an unknown but potential risk for adverse events in nursing infants secondary to treatment of the mother with ublituximab breastfeeding should be discontinued if the mother is enrolled.

Number of subjects	Five (5) subjects will be enrolled to receive UTX + steroids.
Populations	
Intention-To-Treat (ITT) – all subjects who received one dose of trial medication (UTX)
 
Per Protocol (PP) – all subjects who performed all visits in accordance with protocol without significant protocol deviations or violations
 
Safety Population – all subjects that receive one dose of trial drug (UTX)

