Statistical issues	
Primary Safety Assessments: A summary of the number and percentage of subjects with any adverse event (AE), any serious adverse event (SAE), adverse events leading to permanent discontinuation of trial drug and trial drug-related adverse events will be reported.
 
Secondary Efficacy Assessments: Change in neurologic outcomes on the EDSS, Timed 25-Foot Walk and HCVA scales from admission to discharge (Day 5 or 21), and follow up (Days 90 and 180) will be analyzed by paired t-tests with significant p-values considered less than 0.05. A clinical neurologic improvement is commonly

	observed in > 66% of NMO subjects treated at the Johns Hopkins Hospital. The degree of improvement in this trial population has not been adequately quantified historically. By MRI, length of T2 hyper-intensity and length of T1-post contrast enhancement should be stable or reduced by discharge. A paired t-test will be used to compare these values with significance considered at p-values less than 0.05.
Sample size	The sample size of 5 subjects in this single arm study (UTX + steroid) is based on feasibility and logistical considerations on the number of subjects that will ensure a reliable safety report of ublituximab-mediated B cells depletion in the NMO patient population. An independent Data and Safety Monitoring Board (DSMB) will be composed of five members with at least one member who is an Infectious Disease Specialist, Hematologist, Neurologist, Statistician, and another independent expert with experience on assessing safety. Three of the DSMB members will be on staff at the Johns Hopkins University. The DSMB will be reviewing the safety data after the first two subjects are enrolled and completing the Steroid Treatment Phase to determine if it safe to continue the trial. The DSMB will submit their findings to the Sponsor after every meeting and to the IRB. DSMB meetings can be in-person or via teleconference or a combination of the both. The data to be used for review by the DSMB will be actual raw data recorded in the database. The clinical data will be monitored by TG Therapeutics and will be query-free prior to review by the DSMB.
Duration of Subject Participation	Up to 9 months

Abbreviations and Definition of Terms	
Ab	Antibody
ADCC	Antibody-Dependent Cellular Cytotoxicity
AE	Adverse Event
ALP	Alkaline Phosphatase
ALT	Alanine aminotransferase
AQP4	Aquaporin-4
AST	Aspartate aminotransferase
ATC	Anatomic Therapeutic Class

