4. An improvement in visual acuity using bedside Snellen chart of ≥ 2 lines.

If subjects do not require escalation to plasma exchange because they fulfill the clinical criteria above, an MRI may be performed to confirm resolution of the inflammatory lesion, according to standard of care at Johns Hopkins. Based on the MRI and other clinical factors, the treating physician may proceed to discharge the subject home or change the plan to escalate immunosuppression to plasma exchange for continued treatment of the acute exacerbation.

Findings by MRI that may influence escalation to plasma exchange typically include extension of enhancement, involvement of new areas of the nervous system or an increase in the area of T2 hyperintensity. Historically among the NMO/NMOSD subjects treated at Johns Hopkins, approximately 50% of NMO/NMOSD subjects improve from a relapse with steroids alone. The other 50% require escalated care with plasma exchange.

Before discharge from the hospital, the subject will be scheduled for follow up in the NMO Clinic in 90 and 180 day visits. In addition, subjects will be sent to a local lab for monthly CD19 monitoring until the B cell counts replete to a minimum of 0.5% for patients who will continue to be treated with B-cell depleting agents for preventive care, according to standard of care, or to a minimum of 5% for patients who will use other preventive strategies. These results will be reviewed by the PI, [name].

Plasma Exchange Treatment Phase

Should subjects not meet above clinical criteria to be discharged home, escalation to treatment with plasma exchange is standard of care.

The plasma exchange treatment phase begins at the end of the Steroid Treatment Phase and will last up to 14 days. During the Plasma Exchange Treatment Phase, subjects will undergo 1.0 – 1.5 volumes of plasma exchange every other day according to standard of care. At the end of this phase, a second MRI may be performed to confirm resolution of the lesion, according to standard of care. If any further acute immunosuppressive treatment for the acute NMO flare is required and provided according to standard of care, the subject will continue to be followed for safety issues, but the clinical efficacy data will not be included in the statistical analysis. Historically among NMO/NMOSD

subjects treated at the Johns Hopkins Hospital, approximately 95% of NMO/NMOSD subjects who complete plasma exchange are discharged following completion of the plasma exchange.

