10.1 DEFINITIONS

Intent-to-Treat. All subjects who receive one dose of trial drug will be included in the intent-to-treat group.

Per-Protocol. All subjects who performed all visits in accordance with protocol without significant protocol deviations or violations.

All Subject Treatment Group. All subjects who received one dose of trial drug (UTX).

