11.2 GENERAL ANALYSIS CONVENTION

Interim Analysis

There will be no interim analysis.

Statistical Analysis

A summary of the number and percentage of subjects with any adverse event, any serious adverse event, adverse events leading to permanent discontinuation of trial drug, and trial drug-related adverse events will be reported.

Change in neurologic outcomes on the EDSS, Timed 25-Foot Walk and HCVA scales from admission to discharge will be analyzed by paired t-tests with significant p-values considered less than 0.05.

By MRI, length of T2 hyperintensity and length of T1-post contrast enhancement should be stable or reduced by discharge. A paired t-test will be used to compare changes in these values with significance considered at p-values less than 0.05.

Continuous data will be described using the following descriptive statistics: n, mean, median, minimum and maximum. Data will be displayed in all listings sorted by subject number.

When count data are presented, the percentage will be suppressed when the count is zero in order to draw attention to the non-zero counts. A row denoted "Missing" will be included in count tabulations where necessary to account for dropouts and missing values. Unless otherwise specified, the denominator for percentages will be the number of subjects with a non-missing assessment within the analysis population of interest.

SAS Version 9.2 will be used to perform all analyses.

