11.3 ANALYSIS POPULATIONS

The Intent-to-Treat (ITT) population will be used for the official analysis.

The Safety Population will include all subjects who received one dose of trial drug (UTX). All safety assessments including toxicity will be performed on the Safety Population.

The Per-Protocol Population (PP) will consist of all ITT subjects without a major protocol deviation or protocol violation. The criteria for a major protocol deviation or violation will be determined and documented prior to data base lock. Subject exclusion from the PP population will also be determined and documented prior to database lock. Supportive analyses may be performed based on the PP population.

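### Dosed subjects given further acute immunosuppression after plasma exchange lose their clinical efficacy data, although the ITT set named for the main analysis keeps every dosed subject

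*Combined protocol and SAP*

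**What the plan says.** The exclusion appears three times in the combined protocol and SAP: in the Synopsis, in Section 1.4 and in Section 7, each time in the account of the plasma exchange phase. If the flare needs more acute immunosuppression, "the subject will continue to be followed for safety issues, but the clinical efficacy data will not be included in the statistical analysis".

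The analysis populations are set out elsewhere. Section 10.1: "All subjects who receive one dose of trial drug will be included in the intent-to-treat group". The Populations entry of the Synopsis agrees. Section 11.3: "The Intent-to-Treat (ITT) population will be used for the official analysis". The same section says "All safety assessments including toxicity will be performed on the Safety Population" and gives the per-protocol set a supportive role only.

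The endpoints affected are the changes in EDSS, Timed 25-Foot Walk and HCVA. Section 11.2 says that changes from admission to discharge "will be analyzed by paired t-tests with significant p-values considered less than 0.05". The Synopsis (Statistical issues) extends the same test to Days 90 and 180. Section 11.9 makes the Day 90 change the primary efficacy contrast. Neither 11.2 nor 11.9 mentions the exclusion or a modified ITT set. Section 11 promises a separate SAP with further detail on data handling.

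**The concern.** A dosed subject belongs to the ITT set by definition. Safety has its own population and per-protocol is supportive, so the ITT statement in 11.3 most naturally governs efficacy. The exclusion then removes from that analysis someone whom the population definition includes.

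The exclusion depends on what happens after dosing. The documents do not call further treatment a sign of non-response, but a subject who needs it after steroids, ublituximab and plasma exchange is more likely than not to be doing badly. If so, the remaining paired changes look better than those of all dosed subjects.

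The rule also has no time limit. Read literally, it discards the Day 5 change, which is recorded before plasma exchange starts on Day 6. Its reach is unclear for MRI: the Synopsis and Section 10 class MRI as an objective endpoint, apart from the clinical ones, while Section 2.2 lists it among additional clinical endpoints.

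**Working it through.** **The two rules side by side.** Take a dosed subject who has plasma exchange and then further acute immunosuppression.

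| Source | Subject's EDSS, walk and HCVA data |
|---|---|
| 10.1 and Synopsis Populations, with 11.3 | in the analysis |
| Synopsis, 1.4 and 7 (plasma exchange phase) | not in the analysis |
| 11.2 and 11.9 | no statement |

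The plan gives no figure for how often this happens, so there is nothing of its own to reproduce. The size is worked out below.

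**How often.** Inputs: five subjects (11.1); about 50% escalate to plasma exchange, and about 95% of those who complete it are then discharged (Section 7, historical site figures). Assumption: the 5% not discharged stand in for those given further treatment.

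- Per subject: 0.50 × 0.05 = 0.025
- Expected exclusions: 5 × 0.025 = 0.125
- At least one of five: 1 − 0.975^5 = 0.119
- At least one of the four expected completers (11.1): 1 − 0.975^4 = 0.096
- If 1% of escalated subjects get further treatment: 1 − (1 − 0.005)^5 = 0.025
- If 10% do: 1 − (1 − 0.05)^5 = 0.226

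**Effect of dropping one of five.** This was simulated with 2,000,000 sets of five independent N(0,1) changes. The test is a one-sample t-test on the changes at 0.05. The plan does not state sidedness, so two-sided is assumed. The rejection column counts favourable results only, with no true change.

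| Subject dropped | Mean shift toward benefit | Favourable rejection |
|---|---|---|
| none (n = 5) | – | 2.5% |
| worst | 0.29 SD | 8.3% |
| second worst | 0.12 SD | 1.2% |
| median | 0 | 0.8% |

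The mean shifts hold whatever the true mean change. Rejection falls in the last two rows because n drops to four.

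**Overall false favourable rate**, treating any exclusion as one subject:

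- worst always dropped: 0.881 × 0.025 + 0.119 × 0.083 = 0.032
- second worst: 0.881 × 0.025 + 0.119 × 0.012 = 0.0235
- median: 0.881 × 0.025 + 0.119 × 0.008 = 0.0230

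**Precision.** The 95% half-width in sample SDs is 2.776/√5 = 1.24 with five subjects, 3.182/√4 = 1.59 with four and 4.303/√3 = 2.48 with three.

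**Illustration with invented values.** EDSS changes of −1, −1, −1.5, −0.5 and +1 have mean −0.6 (p = 0.235). Without the last subject the mean is −1.0 (p = 0.016).

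**The case against.** The strongest reply is that the rules can coexist. The ITT definition says who is in the set, and the exclusion says which data of a member are not analysed. A specific rule, stated the same way three times, could be read as qualifying the general one. Section 11.2 already allows for missing values in count tables, and 11.3 never expressly ties its main analysis to efficacy. This reading is possible, but it leaves a selection made after dosing under the ITT label, in an analysis section that does not mention it.

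Second, the exclusion may be meant to remove values confounded by other therapy, since Section 5.2 restricts other agents for the relapse. That is a legitimate choice of what to estimate, and retained late values would indeed mix in the later treatment, possibly toward benefit. It does not justify dropping values recorded before that treatment, and the choice needs a name.

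Third, the effect is small. There is about an 88% chance that nobody is excluded, the endpoints are secondary, Section 11.1 relies on summary statistics, and in a five-subject trial the listings should expose any exclusion. With the four expected completers reduced to three, favourable rejection is 7.4% if the worst is dropped and 0.6% if the second worst, so the case is no stronger there. All of this stands and limits the severity.

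Fourth, the MRI ambiguity rests on Section 2.2 alone. It is real but minor.

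**Conclusion.** The concern holds. The efficacy analysis set is not determined by the plan as written, and one of the two readings selects on an event after dosing. The main harm is a mean change that may be biased toward benefit, by up to 0.29 SD on average when one of five is dropped, and an interval about 28% wider relative to the sample SD (1.59/1.24 = 1.28). It is not a large rise in false positives.

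The roughly 12% chance of an exclusion rests on non-discharge as a proxy for further treatment and on approximate historical rates in patients not described as having received ublituximab. The range for the proxy alone is 2.5% to 22.6%. The direction of bias rests on further treatment marking a poor outcome, which the documents do not state. The shifts assume normally distributed changes. The correction should be made, but nothing here touches the primary safety analysis.

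**What to change.** 1. State in Section 11 that the ITT efficacy summaries use the observed values of all dosed subjects, including Day 5 and anything else recorded before further treatment.
2. Replace the exclusion sentence in the Synopsis, 1.4 and 7 to match.
3. Flag subjects given further acute immunosuppression and report their number.
4. Show results without them only as a supportive analysis on a named modified ITT set, noting that values after further treatment may reflect it.
5. Confirm that the Day 90 and Day 180 efficacy assessments apply to these subjects, and say whether MRI follows the same rule.

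The cost is wording in three places and a few sentences in Section 11. Sections 7 and 9 already schedule the Day 90 and 180 tests without exception, so no visit is added if item 5 is confirmed. The mean change may look slightly less favourable, and retained late values may carry the effect of later therapy. The flag and the supportive analysis make that visible. No treatment rule changes.

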5.4 DURATION OF FOLLOW UP

After discharge from the hospital, subjects will be followed as an outpatient clinically at days 90 and 180. In addition, subjects will be monitored monthly for B cell counts for as long as it takes for B cells to replete to a minimum of 0.5% for patients who will continue to be treated with B-cell depleting agents for preventive care, according to standard of care, or to a minimum of 5% for patients who will use other preventive strategies. For most subjects, the duration of B-cell depletion with UTX is up to 9 months. Subjects removed from the trial for unacceptable adverse event(s) will be followed until resolution or stabilization of the adverse event. In addition, subjects will be checked by complete blood count with differential and complete metabolic profile for evidence of toxicity to other cells (e.g., neutrophils) or organs such as kidney or liver function.

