7 TRIAL ASSESSMENTS AND TREATMENT

Given the severity and the consequences of a relapse in NMO, use of an active treatment is considered mandatory. The potential of currently utilized drugs and techniques to reduce the inflammation in NMO has been established primarily through expert consensus and small open label and retrospective studies.

This is Phase 1, unblinded safety trial in NMO/NMOSD subjects in which subjects will receive one (1) infusion of 450 mg of intravenous ublituximab at the onset of an NMO exacerbation in addition to standard of care treatment with daily intravenous methylprednisolone at 1000 mg for five days.

The trial phases and durations, as well as standard of care treatment and MRIs are shown in the table below. For those who complete the trial, it is comprised of 4 potential phases: Screen, Steroid Treatment, Plasma Exchange (if necessary) Treatment and Follow-Up.

Table S1: Ublituximab in NMO Trial Phases and Timings of Treatments/MRIs

Phase:	Screening 1 day	Steroid Treatment* 5 days					Plasma Exchange (if necessary)	Follow-up Monthly	Follow-up 90-Day Visit	Follow-up 6 Month Visit
Day	0	1	2	3	4	5	6-20	30, 60, 90, 120, 150, 180, 210, 240, 270	90	180
Treatment		T ^{1,2}	T ¹	T ¹	T ¹	T ¹				
Exam/Lab	E/L	E/L	L	L	L	E/L	E/L	L	E	E
MRI of affected area	M					M	M		M*	

T1: Administration of methylprednisolone 1000 mg intravenously
T2: Administration of 450 mg of ublituximab intravenously
E: Neurological examination
L: Lab testing
M: MRI, as indicated by standard of care; M*: MRI for research purposes

Screening Phase

The purpose of the Screening Phase is to assess subject eligibility. This process includes an MRI scan (standard of care) to identify a contrast enhancing lesion(s) in the optic nerve and/or spinal cord.

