
Follow-up

The primary outcome is safety for the duration of the period of B cell depletion. Secondary efficacy outcomes will be assessed at follow up 90 and 180 days after initial hospitalization for the acute relapse. In addition to a thorough history and physical examination, including EDSS rating, visual examination and timed walk, a research MRI of the spine will be performed at day 90 to compare to the relapse lesion. In addition, subjects will be sent to a local lab for monthly CD19 monitoring until the B cell counts replete to a minimum of 0.5% for patients who will continue to be treated with B-cell depleting agents for preventive care, according to standard of care, or to a minimum of 5% for patients who will use other preventive strategies. These results will be reviewed by the PI, [name].

Withdrawal

For subjects who discontinue or withdraw from the trial, investigators will continue to monitor subjects who have ongoing neurologic deficits while the subject remains in the hospital. This involves periodic neurologic exams and close observation in collaboration with the treating physician.

Subjects unable to tolerate ublituximab will be withdrawn from the trial. A tolerability issue for the purpose of withdrawing to alternative treatment is defined as a moderate or severe side-effect or complication related to treatment, which is unacceptable to the subject; or a clinically significant change in hematologic, hepatic, or renal laboratory parameters that, in the opinion of the investigator, would require a change in treatment.

Definition of Completer and Maximum Duration of Participation

A completer is defined as a subject who has completed all of the clinically necessary phases of the trial, as per standard of care, and has followed up in the NMO Clinic for all follow up visits. The maximum duration of participation is up to 9 months for most subjects.

Magnetic Resonance Imaging in the Trial

The trial will utilize MRI for spine imaging with and without contrast during the trial for relapses, as per standard of care and for research purposes on 90-day follow-up. In cases of poor creatinine clearance, contrast will not be used. According to standard of care, MRI scans in the trial will be performed at the initiation of the relapse. On follow up, the MRI is a research procedure. For purposes of this trial, standard of care MRIs of the spine will be reviewed by trial staff; the following characteristics will be recorded for research purposes:

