12.10 IMMUNOGENICITY AND PHARMACOKINETICS

12.10.1 Pharmacokinetic (PK) Sampling:

Patients will have pharmacokinetic (PK) sampling (serum) performed as noted on the schedule below:

Time point
Pre-dose
1 min prior to EOI
30 min post EOI ¹
6 hour post EOI ²

24 hour post EOI ³
72 hour post EOI ³
168 hour post EOI ³

EOI: End of Infusion

¹ +/- 5 minutes

² +/- 30 minutes

³ +/- 2 hours

PK Sampling Procedures - IMPORTANT

Stop and start times of UTX infusion must be recorded and actual time/dates of samples drawn must be provided. The subject will not receive any additional infusions of ublituximab.

All samples to be obtained for PK analysis of ublituximab will be serum. One 6-ml blood sample is required for each sample time point.

After centrifugation, 2 aliquots of 0.5 ml of serum should be stored at -20°C to 70°C at the site. One aliquot will be sent to TG Therapeutics and the second aliquot will be shipped to TG Therapeutics after the first sample is received by them. All samples must be sent within 14 days of being collected from the subject.

Approximately seven (7) samples over 7 days should be collected for the PK analysis of ublituximab.

12.10.2 PK Sample Collection and Processing:

- a. Peripheral blood is to be drawn into heparinized vacutainer tubes. The patient's initials, time sample obtained, and date sample was obtained should be recorded on each tube as well as on the respective PK timesheet in the CRF.
- b. Within 20 minutes of collection, centrifuge the blood samples at 900xg for 15 minutes to separate plasma.
- c. For each sample collected, pipette duplicate aliquots of plasma, 2 ml each, in polypropylene cryovials (Nunc). Aliquot 1 is the sample and aliquot 2 is the duplicate.
- d. Aliquots are to be frozen and stored at -20°C to -70°C or lower until specimens are shipped to TG Therapeutics. All samples must be shipped within 14 days following collection for further storage and/or analysis.
- e. Specimens can be batched for shipment once all samples have been collected for a patient within 14 days of being collected.

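### Subjects who cannot tolerate the single ublituximab dose are withdrawn from the trial, and no section expressly keeps them in the B-cell counts, visits and samples that the primary safety window needs

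*Combined protocol and SAP*

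**What the plan says.** Section 7 (Withdrawal) gives the rule: "Subjects unable to tolerate ublituximab will be withdrawn from the trial". The next sentence defines intolerance in different terms: "A tolerability issue for the purpose of withdrawing to alternative treatment". It has two limbs. One is a moderate or severe treatment-related effect that the subject finds unacceptable. The other is a clinically significant hematologic, hepatic or renal laboratory change that, in the investigator's opinion, calls for a change in treatment. For subjects who leave, the same subsection provides that "investigators will continue to monitor subjects who have ongoing neurologic deficits while the subject remains in the hospital".

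Section 6 plans a single dose, and Section 12.10.1 confirms it: "The subject will not receive any additional infusions of ublituximab".

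Section 5.4 gives removed subjects a sentence of their own: "Subjects removed from the trial for unacceptable adverse event(s) will be followed until resolution or stabilization of the adverse event". The sentence after it begins "In addition, subjects will be checked by complete blood count with differential and complete metabolic profile" and does not say whether removed subjects are included. The Synopsis (Follow-up) sets these two laboratory panels monthly after discharge.

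The primary objective (Section 2.1) covers safety from dosing until circulating B cells return, and Section 7 (Follow-up) repeats this as the primary outcome. Section 11.3 keeps every dosed subject in the Safety Population. Section 11.1 expects one dropout and four completers, and does not replace withdrawals.

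**The concern.** With one planned dose, leaving treatment and leaving the trial are different events. After the infusion there is no more ublituximab to stop, but the subject may remain B-cell depleted for months. Removal from the trial then ends scheduled observation inside the period that the primary outcome is meant to cover.

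The subjects affected are chosen by toxicity, and the trigger overlaps with what the DSMB watches. Section 13 names neutropenia, thrombocytopenia, infection and liver-enzyme elevation; three of these four are laboratory findings, and the second limb of the intolerance definition is a laboratory change. Because panels are drawn monthly after discharge, that limb can be met long after dosing.

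At stake are the date of B-cell repletion, scheduled laboratory values, and the antibody results that Section 12.10.4 plans to correlate with safety. Section 12.6.2 summarizes laboratory results by scheduled visit, and Section 11.2 by default uses non-missing denominators for percentages. Later visits would therefore tend to describe the subjects who tolerated the drug.

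**Working it through.** The plan states no figure to reproduce, and five subjects is a feasibility number. The check is a comparison of passages, followed by a count of what is exposed.

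**Step 1. What survives withdrawal**

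| Item | Rule in the plan | Expressly kept after withdrawal? |
|---|---|---|
| The causative adverse event | To resolution or stabilization (5.3, 5.4, 12.6.3) | Yes |
| Other adverse events | 30 days after stopping or completing treatment; treatment-related only after that (12.6.3) | Yes, by its own terms |
| Serious adverse events | Window to 9 months after treatment (12.7.2) | No exception for withdrawn subjects |
| Neurologic deficits | Monitored while in hospital (7, Withdrawal) | Yes, in hospital only |
| Blood count and metabolic profile | Monthly after discharge (Synopsis; see also 5.4) | Unclear |
| B-cell counts | Monthly until repletion (Synopsis, 5.4, 7) | No |
| Day 90 and 180 visits | After discharge (5.4, 7) | No |
| Antibody samples | Pre-dose and 2, 30 and 60 days after infusion (12.10.4) | No |
| Pharmacokinetic samples | Seven, the last three at 24, 72 and 168 hours (12.10.1) | No |

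**Step 2. How the authors write continued follow-up when they intend it.** For subjects who need further immunosuppression after plasma exchange, Section 7 says "the subject will continue to be followed for safety issues". Intolerant subjects have no equivalent sentence covering the planned schedule.

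**Step 3. Monthly draws exposed.** Table S1 lists Days "30, 60, 90, 120, 150, 180, 210, 240, 270", which is 9 draws. Draws lost = scheduled draws after leaving, up to and including the one that shows repletion. The repletion day is an assumption: Section 5.4 says only that depletion lasts up to 9 months for most subjects.

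| Assumed repletion draw | Leaves before Day 30 | Leaves just after the Day 90 draw |
|---|---|---|
| Day 90 | 90/30 = 3 | 3 − 3 = 0 |
| Day 180 | 180/30 = 6 | 6 − 3 = 3 |
| Day 270 | 270/30 = 9 | 9 − 3 = 6 |

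Nine is the maximum on the tabulated schedule only. Section 5.4 continues counts until repletion, so later repletion would expose more.

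**Step 4. Other samples and visits.** A subject who leaves after Day 2 and before Day 30 has 2 of 3 post-dose antibody samples and both outpatient visits unsecured. A subject withdrawn between the 6-hour and 24-hour pharmacokinetic samples has 3 of 7 unsecured.

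**Step 5. Share of the trial.** One case is 1/5 = 20% of subjects.

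**Step 6. Whether late events occur.** In the earlier CLL study (Section 1.2), drug-related events more than one week after the last infusion occurred in 11/33 = 33% of patients. They were mainly 12 infections and 4 neutropenias, so 12 of those 12 + 4 = 16 were infections. That was another disease, with 4 or 8 weekly doses. It shows that late events happen, not their rate here.

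**The case against.** The best defence is that nothing is lost, because the general text already covers these subjects. Section 5.4 says that subjects will have monthly counts for as long as repletion takes, and makes no exception. It also speaks of following subjects who have been removed from the trial, so removal evidently does not end all observation. Section 5.3 runs stopping therapy and trial removal together, and Section 7 speaks of moving to alternative treatment. On that reading, withdrawal means only stopping treatment.

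This reading is possible but not the natural one. Section 5.4 gives removed subjects a narrower endpoint of their own, Section 7 keeps only in-hospital neurologic monitoring, and the plasma exchange text shows that continued follow-up is written out where it is wanted. If the sponsor does intend the general reading, a short clarification settles the matter.

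Other parts of the defence stand. General adverse event recording stops at 30 days for everyone, so that limit is not caused by this rule. A laboratory change that triggers withdrawal is itself followed to resolution or stabilization if it is recorded as an adverse event. Related late events remain reportable, which matters because most of the late CLL events listed were infections. Some subjects who find an effect unacceptable would leave anyway, so the gain from a change is uncertain. After a switch to another B-cell-depleting agent, later counts would no longer describe ublituximab.

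A reader might infer that all safety follow-up ends at withdrawal. The documents do not support that: Sections 5.3, 5.4, 12.6.3 and 12.7.2 keep event-driven follow-up, and the Synopsis sets a monthly laboratory schedule that may apply.

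**Conclusion.** The point stands in a limited form. As written, the rule takes a toxicity-selected subject out of the trial during the primary safety window, and no section expressly continues the B-cell counts, outpatient visits, antibody samples or remaining pharmacokinetic samples. Without B-cell counts, the end of that subject's window is unknown, although the subject stays in the Safety Population. Whether the monthly blood count and metabolic profile continue is unclear.

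The size is 1 of 5 subjects per case, with up to 9 monthly draws on the tabulated schedule. The documents give no intolerance rate for this population, so no probability of a case is claimed.

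Two stronger inferences should be resisted. One is that the headline adverse event summary is distorted: counts of any and of related adverse events do not change for a subject withdrawn for a related side effect. The other is that the rule costs the trial a subject beyond its plan: Section 11.1 already allows for one dropout. The point is which subject is lost, not how many. The row for missing values in Section 11.2 would make the gap visible but would not recover the data.

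The conclusion assumes that withdrawal from the trial means what it says. Part of the clinical background in Section 1.2 was not available for this check. The change is worth making because it is cheap and uses assessments already planned.

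**What to change.** In Section 7 (Withdrawal), separate stopping or changing treatment from leaving the trial. Suggested text:

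*A decision to stop or change treatment for intolerance does not by itself end trial follow-up. Every subject who received any ublituximab remains in the planned monthly B-cell, blood count and metabolic monitoring until repletion, the Day 90 and Day 180 visits, and the remaining pharmacokinetic and antibody samples, unless consent is withdrawn.*

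Then:

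- State in the Synopsis (Follow-up) and Section 5.4 that the monthly laboratory schedule includes these subjects, and reconcile both with Sections 5.3 and 7.
- Record any other B-cell-depleting agent with its date, and flag later B-cell counts so that they are not read as ublituximab repletion.

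This concerns data collection only. Treatment decisions, the adverse event windows in Sections 12.6.1 and 12.6.3, and the withdrawal of undosed subjects under Section 6 are unchanged.

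The cost is wording, plus assessments already planned for each subject who would otherwise have left: up to 9 local draws on the tabulated schedule (more if repletion is later), the Day 90 visit with its research MRI, the Day 180 visit, and any antibody samples (about 4 mL each) and pharmacokinetic samples (6 mL each) still due. A subject can still decline by withdrawing consent.
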